17.2.2. Secondary objective and endpoints

	Secondary Objectives	Secondary Endpoints
Descriptive-observational objective	Definition of iron overload (including serological markers and MRI definition of iron loading in different tissues: liver, pancreas), tissue reactive iron species and oxidative stress in MDS at beginning of transfusional history.	Absolute values of serum ferritin, transferrin saturation, NTBI, LPI, liver and pancreas MRI and oxidative stress at baseline.
	Efficacy	Absolute change in hepatic iron concentration EOS versus baseline.
	On year evolution of iron overload serologic markers	Absolute and relative changes in serum ferritin and transferrin

		saturation from baseline to every visit during the whole treatment period.
	Presence and quantitative evolution of toxic serum iron forms (iron tissue reactive species) under low dose DFX therapy.	Proportion of patients with NTBI > normal values and/or LPI > normal values at end of study vs baseline. Changes in NTBI and LPI from baseline to every visit during the whole treatment period.
	Verify if regular suppression of the “free iron forms” prevent accumulation of tissue iron.	Relationship between NTBI and LPI with serum ferritin and liver and pancreas iron overload (MRI) at end of study versus baseline
	Evaluate the overall safety of deferasirox FCT formulation in patients with lower risk MDS at the beginning of their transfusional history	Overall safety, as measured by frequency and severity of reported AEs and SAEs and changes in laboratory values from baseline: serum creatinine, creatinine clearance ALT, AST, complete blood count (platelets, RBC and WBC) and total direct and indirect bilirubin).
	Leukemic transformation (progression to leukemia or higher rIPSS scores)	Proportion of patients with a disease progression (progression defined as a transition into a higher MDS risk group based on revised IPSS scoring or progression to AML) Time to progression (defined as above) or to leukemia transformation.
	Hemopoietic response	Percentage of patients with hematologic improvements in term of erythroid response following IWG 2006 criteria. Time to reach transfusion dependence defined as > 2 PRBC units/months for 3 months for patients with pre-transfusional Hb < 9.0 g/dl (or <10 g/dl for patients with cardiac disease) or a total number of PRBC units received = 20 from baseline. Absolute reticulocytes count from baseline to every visit during the whole treatment period. Absolute values and evolution of serum transferrin receptor, GDF11, GDF 15 and erythroferrone from baseline to every visit during the whole treatment period. Evaluation of transfusional ratio: number of units received in a

		predetermined period/ Mean pre-transfusional Hb level. Compared with other studies on general population (study and FISIM-ETS registry). Patients receiving concurrent rHuEpo will not be considered for erythroid response
	Costs analysis	Cost and outcome with low dose in early chelation vs. chelation treatment in MDS patients with transfusional iron overload in accordance with either local or international guidelines
Exploratory objective and endpoint	Study of biological cellular damage by iron toxicity before and during treatment	MDA values during the study and relationship to NTBI and LPI values

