There have been very occasional post-marketing reports of erythema multiforme, leukocytoclastic vasculitis and hypersensitivity reactions (including anaphylaxis and angioedema). Alopecia, usually comprising thinning of the hair, has been occasionally reported in patients receiving deferasirox.

Mild, non-progressive increases in serum creatinine, mostly within the normal range, occurred in about 36% of patients during the first year of treatment. These were dose-dependent, often resolved spontaneously and were sometimes alleviated by reducing the dose. Rare cases of acute renal failure, defined as a serum creatinine increases ≥ 2 ULN, and usually reversible after treatment interruption (and rarely a brief course of hemodialysis), have been reported following the prescription use of deferasirox.

Elevations of liver transaminases were reported as an adverse reaction in about 2% of patients. These were not dose-dependent and most of these patients had elevated levels prior to receiving deferasirox. Elevations of transaminases >10 ULN were uncommon (0.3%). There have been post-marketing reports of hepatic failure, mostly in patients with severe baseline liver disease.

There have been reports of cytopenias, mostly in patients with pre-existing blood disorders which are frequently associated with failure of the bone marrow to produce sufficient amounts of blood cells.

High frequency hearing loss and lenticular opacities (early cataracts) have been uncommonly observed in patients treated with deferasirox. As with other iron chelator treatment, the risk of toxicity of deferasirox may be increased when inappropriately very high doses are given in patients with a low iron burden or with serum ferritin levels that are only slightly elevated. Recent data do not confirm these ocular and hearing toxicity in adults (68).

In summary, deferasirox is a once-daily oral iron chelator that has been developed for treating transfusional iron overload, with demonstrated efficacy in the reduction or maintenance of body iron stores, and an acceptable safety profile.

Recently Deferasirox film coated tablets (DFX FCT) has been released (69) and is progressively substituting the water dispersible tablets.

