16.2. Treatment

According to the label during the first month of treatment renal function (serum creatinine and creatinine clearance) will be checked weekly, liver function (ASL, ALT and serum bilirubin) will be checked every other week).

At any month step and at any transfusional event:

- Physical Examination;
- ECOG;
- Vital Signs;
- Clinical Laboratory Evaluations (see scheduled laboratory examination);
- In addition, at any transfusional event: CBC, Renal function (creatinine and blood urea) and liver function (bilirubin, AST, ALT)
- Peripheral blood immunophenotyping in case of suspicious leukemic dissemination;

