16.6. Schedule of assessments

	Site	Screening	Baseline	Month 1	M 2	M 3	M 4	M 5	M 6	M 7	M 8	M 9	M 10	M 11	EOS
Informed consent	Local	X													
Inclusion /exclusion criteria	Local	X													
Medical history	Local	X													
Physical examination (including height, weight and BSA)*	Local	X	X	X	X	X	X	X	X	X	X	X	X	X	X
Pregnancy test	Local	if indicated					if indicated						if indicated		
ECOG*	Local	X													
CBC (including reticulocytes)	Local	X	X	X	X	X	X	X	X	X	X	X	X	X	X
Creatinine clearance	Local	X	X	X	X	X	X	X	X	X	X	X	X	X	X
Serum Creatinine	Local	X	X	X	X	X	X	X	X	X	X	X	X	X	X
Blood Urea	Local	X	X	X	X	X	X	X	X	X	X	X	X	X	X
Urine proteins (measured in non first void sample urine)	Local	X	X	X	X	X	X	X	X	X	X	X	X	X	X
ASL	Local	X	X	X	X	X	X	X	X	X	X	X	X	X	X
ALT	Local	X	X	X	X	X	X	X	X	X	X	X	X	X	X
Bilirubin	Local	X	X	X	X	X	X	X	X	X	X	X	X	X	X
Serum Ferritin	Local	X	X	X	X	X	X	X	X	X	X	X	X	X	X
Transferrin saturation	Local	X	X	X	X	X	X	X	X	X	X	X	X	X	X
Serum Erythropoietin	Local	X	X			X			X			X			X

Ophthalmology examination**	Local	X													X
Audiometry**	Local	X													X
12 Lead ECG	Local	X													X
Echocardiography	Local	X													X
Marrow aspiration (WHO 2016 criteria) or biopsy	Local	If clinical indicated													X
QoL Questionnaire	Local		X								X				X

§During the first month of treatment additional laboratory checks must be performed: serum creatinine and calculated creatinine clearance every week, transaminases and serum bilirubin every two weeks (according to SmPC – RCP)

Concomitant Medications	Recorded from the screening through 30 days after the last dose of treatment
PRBC transfusions	A standard pre-transfusional Hemoglobin level will be indicated (Hb threshold for transfusion Hb 9 g/dl or 10 g/dl for patients with cardiac disease) to be maintained during the study year. Pre transfusional hemoglobin level and transfusions date and frequencies will be recorded. A transfusional ratio will be determined: number of units received in a predetermined period/ Mean pre-transfusional Hb level
Adverse events	Recorded from the first dose of study drug through last patient last visit
Serious Adverse Events	Recorded from signing of the informed consent form through last patient last visit

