18. SAFETY MONITORING AND REPORTING

Safety monitoring will be based on the i) evaluation of changes from baseline throughout the whole study in physical examination, heart rate/rhythm, blood pressure, renal function, liver function and laboratory findings, ii) a global assessment of organ function; and iii) the observation and report of any adverse event (AE).

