20.2. Sample size calculation

Including 50 subjects in the study, we can reach almost 60% power to detect small effect size 0.30 (with p value of 0.05) whereas, we have almost 100% to detect moderate effect size of 0.50 (with p-value of 0.05). On the basis of previous experience, the low dosage, the early intervention and the FCT preparation a 20% drop out rate is expected (10 additional patients to be enrolled)

Methods:

The power test was performed by G power 3.1 software by using the t test Means: Difference between two dependent means (matched pairs).

As demonstrated by our sample size analyses, we have enough power to detect an effect size between 0.3 and 0.5 considering a potential error of 0.05, which is largely accepted from scientific community.

The effect size is calculated on a common scale by G-power program which allows to compare the effectiveness of different variables on the same outcome. In other words, quantifies the magnitude of the difference of a variable between two population groups.

To interpret the resulting number, most scientists use this general guide developed by Cohen:

- < 0.1 = trivial effect
- $0.1 - 0.3$ = small effect
- $0.3 - 0.5$ = moderate effect
- > 0.5 = large difference effect

20.3. Statistical method and data analyses.

Analysis population: the planned enrolment target is 50 patients (+ 20% drop out rate) for a total number of 60 patients.

Data from all centers participating in this study will be pooled for analyses.

Standard descriptive analyses will include:

- Frequencies and percentages for categorical data;
- n, mean, standard deviation, minimum, median, 25th and 75th percentiles and maximum for continuous data.

Whenever possible, the analysis will be performed by visit.

Analysis sets

Full Analysis Set (FAS): All enrolled patients.

Safety analysis set (SS): All enrolled patients who will have received at least one dose of study drug and have at least one post-baseline safety assessment. Note that an entry on the Adverse Event CRF of a statement that a patient had no adverse events constitutes a safety assessment.

Per Protocol analysis set (PP): All enrolled patients who will have received at least one dose of study drug without any major protocol violations and complete the treatment study phase or withdraw from the study due to unsatisfactory therapeutic effect.

Patient demographics/other baseline characteristics

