Demographic and other baseline data (including disease characteristics and transfusion history, etc) will be summarized descriptively for the Safety analysis set by means of the statistics above mentioned. Summary tables will be provided about medical history coded by System Organ Class and Preferred Term of MedDRA dictionary.

Treatments (study treatment, concomitant therapies, compliance)

The descriptive analysis listed below will be reported for the safety analysis set.

Study drug

The duration of study drug exposure, as well as average prescribed doses, will be summarized. Any dose adjustments and reasons that led to the adjustments will be listed. The number and duration of dose interruptions will also be described.

Compliance

Compliance based on prescribed amount of study medication versus amount of medication taken based on dispensed and returned amount of study medication will be summarized.

Concomitant Therapies

Concomitant medications and significant non-drug therapies prior to and after the start of the study treatment will be coded by WHO Drug Reference List dictionary and frequencies will be calculated according to drug classes.

The primary objective is prevention of iron accumulation measured by (primary variable) Change of hepatic iron from baseline according to baseline hepatic iron level: Baseline versus end of study.

For patients with baseline LIC ≤ 5 mg/g dry weight (dw) ± 1.5 mg/g dw.

For patients with baseline LIC > 5 mg/g dw $\pm 20\%$ (by R2- MRI ; test performed in a 1.5 tesla MRI machine and analyzed following R2 method (75).

The corresponding secondary efficacy variable will be the absolute change in hepatic iron concentration EOS versus baseline.

Difference between baseline versus EOT will be measured as continuous variables and analyzed with parametric or non parametric statistical tests depending by normality of distribution.

Secondary endpoint:

Observational: demographics and other baseline characteristics will be study with descriptive statistics. Analysis will be done on FAS and PP.

As the same way secondary endpoints will be evaluated as continuous or nominal variables and analyzed accordingly with parametric or non parametric tests. Efficacy parameters analysis will be done on FAS and PP.

Final Safety parameters will be measured in full analyses set and in all patients who received at least one dose of study drug (safety set).

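### The planned laboratory safety summaries do not count how many patients ever had a relevant abnormality, and no rule places off-schedule results in them

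*Combined protocol and SAP*

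**What the plan says.** - **Endpoint.** Section 17.2.2, like the synopsis, defines safety as "Overall safety, as measured by frequency and severity of reported AEs and SAEs and changes in laboratory values from baseline". The tests named are creatinine, creatinine clearance, ALT, AST, blood count (platelets, RBC, WBC) and bilirubin.
- **Method.** Section 20.3 has no paragraph on laboratory analysis. Its general rules are "n, mean, standard deviation, minimum, median, 25th and 75th percentiles and maximum for continuous data" and "Whenever possible, the analysis will be performed by visit". On safety it names only the analysis sets: "Final Safety parameters will be measured in full analyses set and in all patients who received at least one dose of study drug (safety set".
- **Monitoring.** Section 18 rests safety monitoring on "evaluation of changes from baseline throughout the whole study" and on adverse event reports.
- **Tests outside the monthly grid.** Section 16.2 requires, "at any transfusional event: CBC, Renal function (creatinine and blood urea) and liver function (bilirubin, AST, ALT". A note to the schedule in Section 16.6 says "During the first month of treatment additional laboratory checks must be performed": creatinine and creatinine clearance weekly, transaminases and bilirubin every two weeks. Section 16.4 adds laboratory tests at early withdrawal.
- **Expected signal.** Section 8.4 reports creatinine rises in about 36% of patients in the first year, described as mild and mostly within the normal range, and says of them: "These were dose-dependent, often resolved spontaneously and were sometimes alleviated by reducing the dose". It gives about 2% for transaminase elevations.

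**The concern.** A by-visit table of change from baseline describes the group at a point in time. The safety question is about patients: how many ever reached a value that matters, and how bad it was. No worst-value, shift or threshold-incidence analysis is planned, so the stated method cannot give that count.

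Three features of this trial make the gap matter. It has a single arm, and Section 9 hypothesises better tolerability, so its results will be read against the per-patient rates in Section 8.4. Creatinine rises on this drug are said to resolve often, so a rise may be missed by, or diluted in, a monthly column. And Section 15.1 lists an abnormal laboratory value among the reasons to discontinue treatment, so an affected patient may be absent from later columns.

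The transfusion-day and early extra tests may be the ones that catch a short episode. Without an assignment rule, whether they appear in any table depends on how the programmer reads the plan.

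**Working it through.** The plan gives no figure on this point to reproduce. The calculations below illustrate size only. The size, timing and length of a rise are assumptions.

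**1. What a visit summary shows when several patients are affected.** Assume 50 patients measured at a visit (the evaluable number in Section 11.2), all starting at 0.9 mg/dl, with 5 of them doubling to 1.8 mg/dl.
- Largest shift in the visit mean, with all five raised at the same visit: 5 × 0.9 / 50 = 0.09 mg/dl.
- If the five have resolved, or no longer attend, the shift is 0.
- The 75th percentile does not move, because only 5/50 = 10% of values are raised.
- The maximum is 1.8 mg/dl whether one patient or five doubled.
- A worst-value table shows 5/50 = 10%, exact binomial 95% CI 3.3% to 21.8%.

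**2. The same check using the protocol's own incidence.** Take 36% of the 60 enrolled patients: 0.36 × 60 = 21.6. Let each have one raised value, spread evenly over the 12 post-baseline columns of Section 16.6 (months 1 to 11 and end of study).
- Patients raised at any one visit: 21.6 / 12 = 1.8.
- Shift in each visit mean = 0.36 × rise / 12. A rise of 33% gives 1.0%, 50% gives 1.5% and 100% gives 3.0%.
- The patient-level incidence is 36% in every case.

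**3. Whether off-schedule tests carry information.** For an episode of d days and k independent, randomly timed tests per 30.4-day month, the chance that at least one test falls within it is 1 − (1 − d/30.4)^k.

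| Episode | Monthly test only (k = 1) | One extra test (k = 2) | Two extra tests (k = 3) |
|---|---|---|---|
| 7 days | 23% | 41% | 54% |
| 14 days | 46% | 71% | 84% |

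On these assumptions, one extra test a month raises the chance of catching a one-week episode from 23% to 41%. Placing these results in the tables is therefore more than a formality.

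**4. Can the adverse event route supply the count?** Section 18.1 includes laboratory abnormalities that amount to adverse events, allows detection between visits or by laboratory test, and requires a CTCAE grade. It does not say at what value, or on whose judgement, an abnormality becomes an adverse event. It cites CTCAE 4.03, while Appendix B cites version 5.0. The route exists, but its counts depend on unstated judgement and an unsettled scale.

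**The case against.** The strongest defence is that patient-level safety is already covered. Adverse event frequency and severity come first in the endpoint. A patient whose creatinine doubled and who then stopped could still appear in the adverse event tables, and Section 20.3 also summarises dose interruptions. The independent committee in Section 21 reviews safety data during the trial. The roughly 2% transaminase figure is itself an adverse-reaction rate, so the adverse event table is its natural counterpart. All of this stands. It is why the gap is moderate, but without a rule for turning a laboratory value into an adverse event it does not close the gap.

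A reader might also infer more than the documents support:

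- **That transient toxicity would be averaged away.** Means and quartiles dilute it, but the minimum and maximum are planned and would show an extreme value at any visit to which it is assigned.
- **That transfusion-day tests are left out.** No section excludes them. By-visit analysis is qualified as applying where possible, and Section 18 speaks of the whole study. The plan is silent.
- **That the first-month checks have no visit.** Section 11.1 counts 16 visits plus screening, while the grid in Section 16.6 has 13 columns after screening. Three extra first-month checks would make up the difference, so they may already count as visits. This is an inference.
- **That rises are over by the next monthly visit.** Section 8.4 gives no time course for creatinine and says nothing about transient liver signals. It calls the creatinine rises dose-dependent, and 3.5 mg/kg is the lowest FCT dose in the range in Section 8.5, so 36% may not carry over to this trial.

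**Conclusion.** The point holds as a gap in the analysis plan. Laboratory safety is planned only as change from baseline with general descriptive statistics. The plan neither counts patients who were ever abnormal nor says how off-schedule results are used. By-visit summaries cannot be compared with the incidences in Section 8.4, and they can under-represent rises that resolve between visits or lead to discontinuation.

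The size shown is a mean shift of at most 0.09 mg/dl against 10% of patients affected. It rests on an assumed doubling in 5 of 50 patients, all 50 measured, and a common baseline of 0.9 mg/dl. It shows how much a visit mean can conceal and is not a forecast for this trial. The detection percentages rest on assumed episode lengths and random test timing.

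The primary endpoint is unaffected and no new data are needed. The change should be made because it is cheap and gives a better answer to the safety question.

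**What to change.** In Section 20.3, add a laboratory safety paragraph for the safety set:

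1. Report each patient's worst post-baseline value (the lowest where low is adverse) and a baseline-to-worst grade shift table for creatinine, creatinine clearance, ALT, AST, bilirubin, platelets and WBC. Add neutrophils if a differential is recorded, since Section 17.2.2 does not name them.
2. Use every result from first dose to 30 days after the last dose: monthly, extra first-month, transfusion-day, unscheduled and early-withdrawal.
3. Define visit windows and say how off-schedule results are assigned in the by-visit tables. Keep those tables as supportive.
4. Report the number of tests per patient beside the worst-value tables.
5. State when a laboratory abnormality is recorded as an adverse event.
6. Before any grading, reconcile the CTCAE version between Section 18.1 and Appendix B.

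The cost is two or three more tables from data already collected, plus a short text change. The downside is that patients transfused more often are tested more often and so have more chances of an extreme value. Item 4 lets the reader see this.

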Study design	
 • This is an open-label, single arm, phase II, study designed to look whether early intervention with low dose DFX improves clinical outcome of patients with MDS. • Efficacy of early - low dose DFX FCT to prevent iron accumulation regularly suppressing reactive oxygen species. • Safety of early low dose DFX FCT. • Exploratory: possibility to guide chelation therapy by NTBI/LPI. • One arm • Fixed dose • Blinding: Open • Structure: Single Group • Randomized: Non-randomized • A standard pre-transfusion Hemoglobin level will be indicated (Hb threshold for transfusion Hb 9 g/dl or 10 g/dl for patients with cardiac disease) to be maintained during the study year. Pre transfusion hemoglobin level and transfusions date and frequencies will be recorded. A transfusional ratio will be determined: number of units received in a predetermined period/ mean pre-transfusion Hb level 	
Duration of the study	Enrolment 1 year. Per protocol treatment: 1 year. Total duration 2 years	
Number of patients	60 (50 + 10 for 20% drop out rate)	
Population	Adult MDS patients (≥ 18 years). Very low, low and intermediate risk group by revised-IPSS. Regularly transfused patients with low PRBC transfusion burden (less than 2 units/months for 3 consecutive months) at beginning of their transfusion story (total number of PRBC units received 5-20). Patients should not meet the published criteria for transfusion dependency (2 PRBC units /month for three consecutive months).	
Inclusion criteria	
Study population:
 
 • Diagnosis: Adult Myelodysplastic Syndrome (≥ 18 years). • Revised IPSS: very low, low – intermediate. 	

	
 Having received 5-20 packed red blood cell units Serum ferritin ≥ 300 ng/ml Transferrin saturation $\geq 60\%$ Chelation naïve Capability to provide informed consent

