11.3. Duration of the study

Patients will be recruited over 12 months and followed for 1 year treatment phase. The anticipated study dates (start / end) are:

- Total accrual period (months/years): 12 months
- The duration of the treatment period is 12 months
- End of the study: last patient last visit.
- The Final Study Report will be provided after the end of the Study.

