12. STUDY POPULATION

12.1. Inclusion criteria

- Diagnosis: adult Myelodysplastic Syndrome (≥ 18 years).
- Revised IPSS: very low, low – intermediate.
- Having received 5-20 packed red blood cell units
- Serum ferritin >300 ng/ml
- Transferrin saturation $>60\%$
- Chelation naïve
- Ability to provide informed consent.

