12.2. Exclusion criteria

- Patients aged <18 years old
- Higher risk MDS (Intermediate 2, high)
- Cumulative transfusional history of > 20 packed red cell units
- To be definitely classified as transfusion depended following published criteria (74) (having received 2 packed red cell units /months for three consecutive months)
- Creatinine Clearance (CrCL): <60 ml/min. Patients with CrCl of 40-60ml/min will be included only individually if no other renal risk factors are present.
- Serum creatinine $>2 \times$ ULN at screening.
- Serum creatinine will be measured at screening (repeatable)
- Significant proteinuria as indicated by a urinary protein/creatinine ratio > 0.5 mg/mg in a non-first void urine sample at screening (repeatable).

- ECOG performance status >2.
- Left ventricular ejection fraction < 50% by echocardiography
- A history of hospitalization for congestive heart failure.
- Systemic diseases which would prevent study treatment (e.g. uncontrolled hypertension, cardiovascular, renal, hepatic, metabolic, etc.)
- Clinical or laboratory evidence of active Hepatitis B or Hepatitis C (see EASL criteria).
- History of HIV positive test result (ELISA or Western blot).
- Treatment with systemic investigational drug within 4 weeks or topical investigational drug within 7 days of study start.
- ANC < 500/ microL
- Platelets transfusion dependency
- ALT or AST >3 x ULN at screening.
- Total bilirubin >1.5x ULN at screening (patients with Gilbert syndrome are allowed to enter the study).
- Diagnosis of liver cirrhosis child score C.
- Patients participating in another clinical trial other than an observational registry study.
- Patients with a history of another malignancy within the past five years, with the exception of basal skin carcinoma or cervical carcinoma in situ or completely resected colonic polyps carcinoma in situ.
- History of non-compliance to medical regimens, or patients who are considered potentially unreliable and/or not cooperative.
- Presence of a surgical or medical condition which might significantly alter the absorption, distribution, metabolism or excretion of study drug.
- Pregnant, intending-to-become pregnant, or breast-feeding patients.
- Women of potential maternity age who do not agree to practice effective contraceptive methods for the entire study duration.
- History of drug or alcohol abuse within the 12 months prior to enrollment.
- Hypersensitivity to the active substance or to any of the excipients.

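### The time-to-transfusion-dependence endpoint requires more than 2 units a month, while entry already counts 2 a month for three consecutive months as dependence, so patients who rise to exactly 2 are scored late or not at all

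*Combined protocol and SAP*

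**What the plan says.** **Endpoint.** Section 17.2.2 (hemopoietic response), repeated in the synopsis, gives "Time to reach transfusion dependence defined as > 2 PRBC units/months for 3 months". It adds a haemoglobin condition, "for patients with pre-transfusional Hb < 9.0 g/dl (or <10 g/dl for patients with cardiac disease", and an alternative route to the event, "or a total number of PRBC units received = 20 from baseline". No source is cited for the rate.

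**Entry.** Section 12.2 excludes patients classified as transfusion dependent by cited published criteria, which it summarises as "having received 2 packed red cell units /months for three consecutive months". The synopsis population says the same: "Patients should not meet the published criteria for transfusion dependency (2 PRBC units /month for three consecutive months". It also describes eligible patients as having a "low PRBC transfusion burden (less than 2 units/months for 3 consecutive months", so exactly 2 a month falls on the dependent side at entry.

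**Context.** Section 12.1 requires "Having received 5-20 packed red blood cell units". Section 11.3 states: "The duration of the treatment period is 12 months". Sections 11.1, 14.5 and 16.6 have transfusion dates and frequencies recorded.

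**The concern.** One term is defined in two ways, and the definitions give opposite answers at 2 units a month. The endpoint is meant to time a patient's move out of the non-dependent state that eligibility requires. Units are whole numbers and entrants sit below 2 a month, so 2 is the first steady whole-number rate at which a worsening patient leaves the entry population. The endpoint's rate condition does not register that move. The endpoint also omits the word consecutive and adds a haemoglobin condition and a 20-unit count, none of which the entry rule shares. No section explains the differences.

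At stake is the date of a stated secondary endpoint, and whether some patients have an event within 12 months. The plan also leaves open whether the rate applies to each month or to a three-month mean, and which units count toward 20. Those choices could be made after the data are seen.

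**Working it through.** The plan states no figure for this endpoint, so there is nothing to reproduce. The check applies both definitions, month by month, to fixed 12-month transfusion histories.

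**Inputs.** Entry rule: at least 2 units in each of three consecutive months (12.2; the words at least are inferred from the synopsis calling less than 2 eligible). Endpoint: more than 2 units a month for 3 months, or 20 units from baseline (17.2.2). Follow-up: 12 months (11.3).

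**Assumptions.** The haemoglobin condition is met; its cut-offs equal the transfusion thresholds in 11.1. The 20-unit count is met when the running total reaches 20. It counts post-baseline units, as literally worded, unless stated otherwise.

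**Distance between thresholds over three months.**
- Entry rule: 3 × 2 = 6 units.
- Endpoint as a three-month mean: at least 7 units, 7/6 = 1.17 (17% more).
- Endpoint with every month above 2: 3 × 3 = 9 units, 9/6 = 1.50 (50% more).

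These ratios compare thresholds; they do not measure bias in the endpoint.

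**Rise to exactly 2 a month.** Let a patient receive *r* units a month for *s* months, then 2 a month. The entry rule is met at month s + 3. The rate condition is never met on any reading. The total at month m is r·s + 2(m − s), so it reaches 20 at m = s + (20 − r·s)/2, rounded up.

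| Earlier rate r | Step-up after month s | Entry rule met | Endpoint met |
|---|---|---|---|
| none | 0 (2 a month from baseline) | 3 | 10 |
| 0 | 1 | 4 | 11 |
| 0 | 2 | 5 | 12 |
| 0 | 3 to 9 | 6 to 12 | not by month 12 (18 units or fewer) |
| 1 | 1 | 4 | 11 |
| 1 | 2 | 5 | 11 |
| 1 | 3 | 6 | 12 |
| 1 | 4 | 7 | 12 |
| 1 | 5 to 9 | 8 to 12 | not by month 12 (19 units or fewer) |

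Two cases in full:
- 2 a month from baseline: 6 units and the entry rule at month 3; 2 × 10 = 20 units and the endpoint at month 10, seven months later.
- 1 a month for six months, then 2: entry rule at month 9; 6 × 1 + 6 × 2 = 18 units at month 12, so no event.

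**If the 20 units include those received before entry.** With 5, 10 or 15 prior units, the first patient is scored at month 8 (5 + 16 = 21), month 5 (10 + 10 = 20) or month 3 (15 + 6 = 21). The second is scored at month 11 (5 + 6 + 10 = 21), month 8 (10 + 6 + 4 = 20) or month 5 (15 + 5 = 20), against month 9 by the entry rule.

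**Other patterns.**
- 2, 3, 2, 3…: entry rule at month 3. As a three-month mean, the endpoint is met at month 3 (7 units). If three consecutive months must each exceed 2, only the 20-unit count applies, at month 8 (running totals 2, 5, 7, 10, 12, 15, 17, 20). If any three months above 2 suffice, month 6.
- 3 every month: month 3 under both definitions.
- 3, 1, 3, 1…: the entry rule is never met. The endpoint is met at month 10 on the 20-unit count (3, 4, 7, 8, 11, 12, 15, 16, 19, 20), at month 5 if any three months above 2 suffice, or at month 3 as a mean (7 units).

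**The case against.** The best defence is that the stricter rate was chosen deliberately, so that the event is a firm one, and that the 20-unit count catches patients who settle at 2 a month. The documents do not say the difference is deliberate. Where the protocol wants a clearly higher rate (more than 4 units a month, section 15.1), it gives the state a different name. The 20-unit count does catch some of these patients, but on the literal reading it does so months later, and it misses later step-ups.

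Other objections stand and limit the point:

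- A reader might infer that everyone who becomes dependent by the entry rule is scored late or never. That is too broad: patients steadily at 3 a month are scored on time. The gap concerns patients at exactly 2 and, where each month must exceed 2, those mixing 2 and 3.
- A reader might infer that the mismatch flatters the drug. The strict inequality alone can only delay or remove events. But the missing word consecutive and the 20-unit count can create earlier or extra events, as the 3, 1, 3, 1 pattern shows. Counting prior units can also put the event before the entry-rule date. The net direction is not established.
- A reader might suppose that exactly 2 a month is common. The documents give no frequency.
- A reader might conclude that the result cannot be compared with studies using the published criteria. Transfusion dates are recorded, so the endpoint can be re-derived under either rule. The external comparison in that table cell follows the transfusional ratio.
- This is one of several measures under one secondary objective, with no target or hypothesis of its own.

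**Conclusion.** The point holds in a limited form. Followed as written, the plan times transfusion dependence by a rule that disagrees with its own entry definition at exactly 2 units a month. For a patient at 2 a month from baseline the endpoint falls at month 10 instead of month 3. With 1 unit a month beforehand, any step-up to 2 after month 5 or later gives no event within 12 months.

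These results assume that the haemoglobin condition is met and that the 20 units are counted from baseline, as worded. If lifetime units count, the seven-month delay becomes five, two or zero months with 5, 10 or 15 prior units. The histories are illustrative; how many patients would follow them cannot be known from the documents. The documents support misdating for an identifiable group, but not a claim about overall bias in either direction. The primary liver iron endpoint and the sample size are not affected. The plan should be corrected before analysis.

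**What to change.** In section 17.2.2 and the synopsis:

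1. Define the rate condition with the entry threshold: at least 2 PRBC units a month in each of three consecutive months, with the event dated at the end of the third month. The patient at 2 a month from baseline is then scored at month 3, and one stepping up after month 5 at month 8.
2. State whether the 20-unit count uses post-baseline or lifetime units, and report events reached only by that route separately.
3. If the haemoglobin condition is kept, say that it is an addition to the entry definition.

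If the higher rate was intended, the alternative is to state and justify it, define the averaging window, and give the endpoint a name that does not repeat the entry term.

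The cost is a few lines of wording. No new data are needed, because transfusion dates and frequencies are already collected. The downside is that the reported time to dependence may be shorter for patients at 2 a month.
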